7.2.5 Sponsor Responsibility for Reporting Adverse Events

All Adverse Events will be reported to regulatory authorities, IRB/IECs and investigators in accordance with all applicable global laws and regulations, i.e., per ICH Topic E6 (R1) Guidelines for Good Clinical Practice.

7.3 TRIAL GOVERNANCE AND OVERSIGHT

7.3.1 Executive Oversight Committee

The Executive Oversight Committee (EOC) comprises members of Sponsor Senior Management. The EOC will receive and decide upon any recommendations made by the external data monitoring committee (eDMC) regarding the trial.

7.3.2 Data Monitoring Committee

To supplement the routine trial monitoring outlined in this protocol, an eDMC (external Data Monitoring Committee) will monitor the interim data from this trial. The voting members of the committee are external to the Sponsor. The voting members of the eDMC must not be involved with the trial in any other way (e.g., they cannot be trial investigators) and must have no competing interests that could affect their roles with respect to the trial.

The eDMC will make recommendations to the EOC regarding steps to ensure both subject safety and the continued ethical integrity of the trial. Also, the eDMC will review interim trial results, consider the overall risk and benefit to trial subjects (see Section 8.7 - Interim Analyses) and recommend to the EOC if the trial should continue in accordance with the protocol.

Specific details regarding composition, responsibilities, and governance, including the roles and responsibilities of the various members and the sponsor protocol team; meeting facilitation; the trial governance structure; and requirements for and proper documentation of eDMC reports, minutes, and recommendations will be described in a separate charter that is reviewed and approved by the eDMC. The eDMC will monitor the trial at an appropriate frequency, as described in the detailed eDMC charter. The eDMC will also make recommendations to the sponsor protocol team regarding steps to ensure both subject safety and the continued ethical integrity of the trial.

8.0 STATISTICAL ANALYSIS PLAN

This section outlines the statistical analysis strategy and procedures for the study. If, after the study has begun, changes are made to primary and/or key secondary hypotheses, or the statistical methods related to those hypotheses, then the protocol will be amended (consistent with ICH Guideline E-9). Changes to exploratory or other non-confirmatory analyses made after the protocol has been finalized, but prior to the conduct of any analysis, will be documented in a supplemental statistical analysis plan (sSAP) and referenced in the Clinical Study Report (CSR) for the study. There will be a separate biomarker analysis plan. Post hoc

03-Nov-2022

Protocol/Amendment No.: 394-06

exploratory analyses will be clearly identified in the CSR. The PRO analysis plan will be included in the sSAP.

Unless specified otherwise, the type I error in Section 8 indicates one-sided type I error.

8.1 Statistical Analysis Plan Summary

Key elements of the statistical analysis plan are summarized in Table 8 below; the comprehensive plan is provided in Sections 8.2 through 8.12.

Table 8 Statistical Analysis Plan

Study Design Overview	A Randomized Double Blind Phase III Study of Single Agent Pembrolizumab plus BSC vs. placebo plus BSC as Second-Line Therapy in Asian Subjects with Previously Systemically Treated Advanced Hepatocellular Carcinoma after Progression on Sorafenib or Oxaliplatin-based Chemotherapy		
Treatment Assignment	Subjects will be randomized in a 2:1 ratio to receive blinded treatment with pembrolizumab plus BSC or placebo plus BSC (Control Arm). Stratification factors are in Section 5.4. This is a double-blinded study.		
Analysis Populations	Efficacy: Intention to Treat (ITT) Safety: All Subjects as Treated (ASaT)		
Primary Endpoints/Hypotheses	Pembrolizumab improves overall survival (OS) compared to placebo.		
Statistical Methods for Key Efficacy Analyses	The primary hypothesis will be evaluated by comparing pembrolizumab to the control on OS using a stratified log-rank test. Estimation of the hazard ratio will be done using a stratified Cox regression model. Event rates over time will be estimated within each treatment group using the Kaplan-Meier method. PFS will be analyzed using the same method for OS. Stratified Miettinen and Nurminen's method [57] with weights proportional to the stratum size will be used for comparison of the objective response rates (ORR) between the treatment arms.		
Statistical Methods for Key Safety Analyses	The analysis of safety results will follow a tiered approach. The tiers differ with respect to the analyses that will be performed. There are no Tier 1 events in this trial. Tier 2 parameters will be assessed via point estimates with 95% confidence intervals provided for between-group comparisons; only point estimates by treatment group are provided for Tier 3 safety parameters. The 95% confidence intervals for the between-treatment differences in percentages will be provided using the Miettinen and Nurminen method [57]		

Protocol/Amendment No.: 394-06

Interim Analyses	Two interim analyses will be performed in this study. Results will be reviewed by an external data monitoring committee. Details are provided in Section 8.7.		
	IA1(ORR-driven):		
	• Timing: to be performed when 163 randomized subjects have at least 24 weeks follow-up (which is estimated to happen at approximately 17 months after study start). Approximately 174 PFS events and 100 OS events are expected to be accumulated.		
	 Purpose: estimate treatment effect and evaluate consistency with global data, interim analysis for ORR, PFS and OS. 		
	IA2 (event-driven):		
	 Timing: to be performed when approximately 276 OS events have been observed and enrollment is complete, estimated to be approximately 31 months after study start. Approximately 395 PFS events are expected to be accumulated at IA2. 		
	 Purpose: interim efficacy analysis for OS and ORR, primary efficacy analysis for PFS. 		
	Final analysis (event-driven)		
	Timing: to be performed when approximately 345 OS events have been observed, estimated to be approximately 37 months after study start		
	Purpose: final analysis for OS, final analysis for ORR.		
Multiplicity	The multiplicity strategy in this study will be applied to the primary hypothesis (superiority of pembrolizumab in OS to placebo) and the secondary hypotheses of superiority of pembrolizumab to placebo in PFS and ORR. The overall Type I error across the three hypotheses above is strongly controlled at 2.5% (one-sided) by the graphical approach of Maurer and Bretz [58] as described in Section 8.8. Initially, α =2.3% will be allocated to the OS hypothesis and α =0.2% will be allocated to the PFS hypothesis. Following a group sequential approach, the Type I error rates for the two interim and final analyses will be controlled through the alphaspending function as described in Section 8.8.		
Sample Size and Power	The sample size is approximately 450.		
	The analyses of OS endpoint is event driven (i.e., the testing of the OS hypothesis is conducted upon accumulating a preset number of events). The study is designed and will be conducted to accumulate approximately 345 OS events (unless superiority in OS is proven at the interim analysis). For primary endpoint OS, the trial has ~87% power to demonstrate that		
	pembrolizumab is superior to the control at a one-sided 2.3% alpha-level, if the underlying hazard ratio of OS is 0.7.		

8.2 Responsibility for Analyses/In-House Blinding

The statistical analysis of the data obtained from this study will be the responsibility of the Clinical Biostatistics department of the SPONSOR.

The SPONSOR will generate the randomized allocation schedule(s) for study treatment assignment for this protocol, and the randomization will be implemented in IVRS.

Protocol/Amendment No.: 394-06

Since the trial is double-blinded with in-house blinding, the Sponsor, the investigators, site staffs, and subjects will be blinded to the treatment assignment. In addition, the blinded central imaging vendor will perform the central imaging review without knowledge of treatment group assignment.

The eDMC will serve as the primary reviewer of the unblinded results of the interim analyses and will make recommendations for discontinuation of the study or modification to an executive oversight committee of the SPONSOR. An external unblinded statistician and statistical programmer will be responsible for generating unblinded data summaries and presenting them to the eDMC. Depending on the recommendation of the eDMC, the Sponsor may prepare a regulatory submission. If the eDMC recommends modifications to the design of the protocol or discontinuation of the study, this executive oversight committee and limited additional SPONSOR personnel may be unblinded to results at the treatment level in order to act on these recommendations. The extent to which individuals are unblinded with respect to results of interim analyses will be documented. Additional logistical details will be provided in the eDMC Charter.

8.3 Hypotheses/Estimation

Objectives and hypotheses of the study are stated in Section 3.0.

8.4 Analysis Endpoints

8.4.1 Efficacy Endpoints

8.4.1.1 Primary

Overall Survival

OS is defined as the time from randomization to death due to any cause. Subjects without documented death at the time of the final analysis will be censored at the date of the last follow-up.

8.4.1.2 Secondary

Progression-Free Survival (PFS) – RECIST 1.1 by BICR

PFS is defined as the time from randomization to the first documented disease progression per RECIST 1.1 based on blinded central imaging vendor review or death due to any cause, whichever occurs first. See Section 8.6.1 for the censoring rules.

Objective Response Rate (ORR) – RECIST 1.1 by BICR

Objective response rate is defined as the proportion of the subjects in the analysis population who have a complete response (CR) or partial response (PR) per RECIST 1.1.

Product: MK-3475 96

Protocol/Amendment No.: 394-06

Disease Control Rate (DCR) - RECIST 1.1 by BICR

DCR is defined as the percentage of subjects who have achieved CR, PR, or have demonstrated SD for at least 6 weeks prior to any evidence of progression based on assessments by the central imaging vendor per RECIST 1.1.

Time to Progression (TTP) – RECIST 1.1 by BICR

TTP is defined as the time from randomization to the first documented disease progression per RECIST 1.1. See Section 8.6.1 for the censoring rules.

Duration of Response (DOR) - RECIST 1.1 by BICR

For subjects who demonstrate CR or PR, duration of response is defined as the time from first documented evidence of CR or PR per RECIST 1.1 until disease progression per RECIST 1.1 or death due to any cause, whichever occurs first.

8.4.2 Safety Endpoints

Safety measurements are described in Section 4.2.3.4 Safety Endpoints and Section 7.

Safety and tolerability will be assessed by clinical review of all relevant parameters including adverse events (AEs), laboratory tests, and vital signs. Safety parameters to be analyzed include, but are not limited to, AEs, SAEs, fatal AEs, and laboratory changes. Furthermore, specific events will be collected and designated as events of clinical interest (ECIs) as described in Section 7.2.3.

Events of clinical interest for this trial include:

- 1. An overdose of Sponsor's product, as defined in Section 7.2.1 Definition of an Overdose for This Protocol and Reporting of Overdose to the Sponsor, that is not associated with clinical symptoms or abnormal laboratory results.
- 2. Hepatic ECIs as defined in Section 7.2.3.

There are no "Tier 1" events in this trial. In addition, the broad clinical and laboratory AE categories consisting of the percentage of subjects with any AE, any drug related AE, any Grade 3-5 AE, any serious AE, any AE which is both drug-related and Grade 3-5, any AE which is both serious and drug-related, dose modification due to AE, and who discontinued due to an AE, and death will be considered Tier 2 endpoints. AEs (specific terms as well as system organ class terms) will be classified as belonging to "Tier 2" or "Tier 3", based on the number of events observed. Membership in Tier 2 requires that at least 4 subjects in any treatment group exhibit the event; all other AEs and predefined limits of change will belong to Tier 3.

Protocol/Amendment No.: 394-06

Analysis Populations

8.5.1 Efficacy Analysis Populations

The Intention-to-Treat (ITT) population will serve as the population for primary efficacy analysis. All randomized subjects will be included in this population. Subjects will be included in the treatment group to which they are randomized.

Details on the approach to handling missing data are provided in Section 8.6 Statistical Methods.

8.5.2 Safety Analysis Populations

The All Subjects as Treated (ASaT) population will be used for the analysis of safety data in this study. The ASaT population consists of all randomized subjects who received at least one dose of study treatment. Subjects will be included in the treatment group corresponding to the study treatment they actually received for the analysis of safety data using the ASaT population. For most subjects this will be the treatment group to which they are randomized. Subjects who take incorrect study treatment for the entire treatment period will be included in the treatment group corresponding to the study treatment actually received. Any subject who receives the incorrect study medication for one cycle but receives the correct treatment for all other cycles will be analyzed according to the randomized treatment group and a narrative will be provided for any events that occur during the cycle for which the subject is incorrectly dosed.

At least one laboratory or vital sign measurement obtained subsequent to at least one dose of study treatment is required for inclusion in the analysis of each specific parameter. To assess change from baseline, a baseline measurement is also required.

Details on the approach to handling missing data for safety analyses are provided in Section 8.6 Statistical Methods.

8.6 **Statistical Methods**

8.6.1 Statistical Methods for Efficacy Analyses

This section describes the statistical methods that address the primary and secondary objectives. Methods related to exploratory objectives will be described in the supplemental SAP.

Efficacy results that will be deemed to be statistically significant after consideration of the Type I error control strategy are described in Section 8.8, Multiplicity. Nominal p-values may be computed for other efficacy analyses, but should be interpreted with caution due to potential issues of multiplicity. In the event that there are a small number of responses in one or more strata, for the purpose of analysis strata will be combined to ensure sufficient number of responses in each stratum. Details regarding the combining of strata will be specified in the sSAP prior to database lock based on a blinded review of response counts by stratum.

03-Nov-2022 Confidential

085/RXM

Protocol/Amendment No.: 394-06

8.6.1.1 Overall Survival (OS)

The non-parametric Kaplan-Meier method will be used to estimate the survival curves. The superiority hypothesis of treatment difference in survival will be tested by the stratified \log rank test. A stratified Cox proportional hazard model with Efron's method of tie handling will be used to estimate the magnitude of the treatment difference (i.e., the hazard ratio). The hazard ratio and its 95% confidence interval from the stratified Cox model with a single treatment covariate will be reported. The stratification factors applied to both the stratified log-rank test and the stratified Cox model will be: macrovascular invasion (Yes, No), α -fetoprotein (ng/mL) (<200, \geq 200) and region (China, ex-China).

Due to the small number in the stratum of presence of macrovascular invasion, subjects from any region or with any level of α -fetoprotein will be combined in this stratum. Thus, the following 5 strata will be used in the stratified log-rank test and the stratified Cox model:

- Macrovascular invasion (No) + Region (China) + α -Fetoprotein (ng/mL) (<200)
- Macrovascular invasion (No) + Region (ex-China) + α-Fetoprotein (ng/mL) (<200)
- Macrovascular invasion (No) + Region (China) + α -Fetoprotein (ng/mL) (≥ 200)
- Macrovascular invasion (No) + Region (ex-China) + α -Fetoprotein (ng/mL) (≥ 200)
- Macrovascular invasion (Yes)

In the event that there are a small number of responses in one or more strata, for the purpose of analysis strata may be further combined to ensure sufficient number of responses in each stratum. Details regarding the combining of strata will be specified in the sSAP prior to database lock based on a blinded review of response counts by stratum.

Prior to verification of PD by blinded independent central review, switching to another treatment is discouraged. Following verification of PD, subjects may switch to another anticancer treatment. Exploratory analyses to adjust for the effect of crossover to other PD-1 therapies on OS may be performed based on recognized methods, e.g. the Rank Preserving Structural Failure Time (RPSFT) model proposed by Robins and Tsiatis [59], two stage model, etc., based on an examination of the appropriateness of the data to the assumptions required by the methods. In case the proportional hazards assumption doesn't hold, supportive analysis using Fleming and Harrington's weighted log-rank test, Restricted Mean Survival Time (RMST) method or other methods, as appropriate, may be conducted, possibly after proper adjustment of the crossover effect over time.

8.6.1.2 Progression-Free Survival (PFS)

The non-parametric Kaplan-Meier method will be used to estimate the PFS curve in each treatment group. The superiority hypothesis of treatment difference in PFS will be tested by the stratified log-rank test. A stratified Cox proportional hazard model with Efron's method of tie handling will be used to estimate the magnitude of the treatment difference (i.e., hazard

Protocol/Amendment No.: 394-06

ratio) between the treatment arms. The hazard ratio and its 95% confidence interval from the stratified Cox model with Efron's method of tie handling and with a single treatment covariate will be reported. The stratification factors and strata applied to both the stratified log-rank test and the stratified Cox model will be the same as those factors and strata used in the stratified analysis for overall survival.

Since disease progression is assessed periodically, progressive disease (PD) can occur any time in the time interval between the last assessment where PD was not documented and the assessment when PD is documented. For the primary analysis, for the subjects who have PD, the true date of disease progression will be approximated by the date of the first assessment at which PD is objectively documented per RECIST 1.1 by blinded independent central review, regardless of discontinuation of study drug. Death is always considered as a confirmed PD event. Sensitivity analyses may be performed for comparison of PFS based on investigator's assessment per RECIST and PFS analysis for PD per irRECIST by blinded independent central review.

In order to evaluate the robustness of the PFS endpoint per RECIST 1.1 by blinded independent central review, we will perform two sensitivity analyses with a different set of censoring rules. The first sensitivity analysis is the same as the primary analysis except that (1) the date of documented PD or death will be the progression date, regardless of whether or not new anti-cancer treatment is initiated and (2) it censors at the last disease assessment, regardless of whether or not new anti-cancer treatment is initiated if no PD and no death occur. The second sensitivity analysis is the same as the first sensitivity analysis, except that it considers discontinuation of treatment due to reasons other than complete response or initiation of an anti-cancer treatment subsequent to discontinuation of study specified treatment, whichever occurs later, to be a PD event for subjects without documented PD or death. The censoring rules for primary and sensitivity analyses are summarized in Table 9.

Table 9 Censoring rules for Primary and Sensitivity Analyses of PFS

Situation	Primary Analysis	Sensitivity Analysis 1	Sensitivity Analysis 2
PD or death documented after ≤1 missed disease assessment, and before new anticancer therapy, if any	Progressed at date of documented PD or death	Progressed at date of documented PD or death	Progressed at date of documented PD or death
PD or death documented after ≥2 consecutive missed disease assessments or after new anticancer therapy, if any	Censored at last disease assessment prior to the earlier date of ≥2 consecutive missed disease assessment and new anticancer therapy, if any	Progressed at date of documented PD or death	Progressed at date of documented PD or death

Protocol/Amendment No.: 394-06

Situation	Primary Analysis	Sensitivity Analysis 1	Sensitivity Analysis 2	
No PD and no death; and new anticancer treatment is not initiated	Censored at last disease assessment	Censored at last disease assessment	Progressed at treatment discontinuation due to reasons other than complete response; otherwise censored at last disease assessment if still on study treatment or completed study treatment.	
No PD and no death; new anticancer treatment is initiated Abbreviations: PD = progress	Censored at last disease assessment before new anticancer treatment	Censored at last disease assessment	Progressed at date of new anticancer treatment	

Addieviations. 1D – progressive disease

The proportional hazards assumption on PFS will be examined using both graphical and analytical methods if warranted. The log[-log] of the survival function vs. time for PFS will be plotted for the comparison between pembrolizumab and the control arm. If the curves are not parallel, indicating that hazards are not proportional, supportive analyses may be conducted to account for the possible non-proportional hazards effect associated with immunotherapies: for example, using the Restricted Mean Survival Time (RMST) method [60], parametric method [61], etc. Further details of the sensitivity analyses will be described in supplemental SAP.

The PFS analyses are described in Section 8.7 Interim Analyses and Section 8.8 Multiplicity. The supportive analysis of the PFS data available at the time of the final OS analysis will be also conducted.

8.6.1.3 Objective Response Rate (ORR)

Stratified Miettinen and Nurminen's method [57] with weights proportional to the stratum size will be used for the comparison of the objective response rates between the treatment arms. A 95% confidence interval for the difference in response rates between the pembrolizumab arm and the control arm will be provided. The stratification factors and strata applied to the analysis will be the same as those factors and strata used in the stratified analysis for overall survival.

The ORR analysis will be conducted according to the hypotheses testing plan as described in Section 8.7 Interim Analyses and Section 8.8 Multiplicity.

8.6.1.4 Disease Control Rate (DCR)

Stratified Miettinen and Nurminen's method [57] with weights proportional to the stratum size will be used for the comparison of the DCR between the treatment arms. A 95% confidence interval for the difference in response rates between the pembrolizumab arm and the control arm will be provided. The stratification factors and strata applied to the analysis will be the same as those factors and strata used in the stratified analysis for overall survival.

Protocol/Amendment No.: 394-06

8.6.1.5 Time to Progression (TTP)

The non-parametric Kaplan-Meier method will be used to estimate the TTP curve in each treatment group. A stratified Cox proportional hazard model with Efron's method of tie handling will be used to estimate the magnitude of the treatment difference (i.e., hazard ratio) between the treatment arms. The hazard ratio and its 95% confidence interval from the stratified Cox model with Efron's method of tie handling and with a single treatment covariate will be reported. The stratification factors and strata applied to both the stratified log-rank test and the stratified Cox model will be the same as those factors and strata used in the stratified analysis for overall survival.

Since disease progression is assessed periodically, progressive disease (PD) can occur any time in the time interval between the last assessment where PD was not documented and the assessment when PD is documented. For the analysis, for the subjects who have PD, the true date of disease progression will be approximated by the date of the first assessment at which PD is objectively documented per RECIST 1.1 by blinded independent central review, regardless of discontinuation of study drug. Unlike in PFS analysis, death is not considered as an event.

The censoring rules for TTP are summarized in Table 10.

Table 10 Censoring rules for TTP

Situation	Primary Analysis	
Death without a preceding disease progression	Censored at date of randomization or date of last non-PD disease assessment, whichever is later	
No PD and no death; new anticancer treatment is not initiated	Censored at last non-PD disease assessment	
No PD and no death; new anticancer treatment is initiated	Censored at last non-PD disease assessment before new anticancer treatment	
PD documented after ≤ 1 missed disease assessment	Progressed at date of documented PD	
PD documented after ≥ 2 missed disease assessments	Censored at last non-PD disease assessment prior to the ≥2 consecutive missed disease assessments	

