8.6.1.6 Duration of Response (DOR)

Subjects who achieved CR or PR and are alive, have not progressed, have not initiated new anti-cancer treatment, have not missed ≥ 2 consecutive disease assessments and have not been determined to be lost to follow-up are considered ongoing responders at the time of analysis.

Protocol/Amendment No.: 394-06

The non-parametric Kaplan-Meier method will be used to estimate the DOR curve in each treatment group; estimates and 95% CIs at specific duration time points will be provided.

Censoring rules for DOR are summarized in Table 11.

Table 11 Censoring Rules for DOR

Situation	Date of Progression or Censoring	Outcome
No progression nor death, no new anti-cancer therapy initiated	Last adequate disease assessment	Censor (non-event)
No progression nor death, new anti- cancer therapy initiated	Last adequate disease assessment before new anti-cancer therapy initiated	Censor (non-event)
Death or progression after ≥2 consecutive missed adequate disease assessments or after new anti-cancer therapy	Earlier date of last adequate disease assessment prior to ≥2 missed adequate disease assessments and new anti-cancer therapy, if any	Censor (non-event)
Death or progression after ≤1 missed adequate disease assessments and before new anticancer therapy, if any	PD or death	End of response (Event)

Subjects are considered to have an ongoing response if censored, alive, have not progressed, have not started a new anti-cancer therapy, have not missed ≥ 2 consecutive disease assessments, and have not been determined to be lost to follow-up.

Table 12 summarizes the primary analysis approach for key efficacy endpoints. Sensitivity analysis methods are described above for each endpoint.

Analyses of the DCR, TTP, and DOR data will be performed at the time of the interim and final analyses of OS.

The strategy to address multiplicity issues with regard to multiple efficacy endpoints, multiple populations, and interim analyses is described in Section 8.7 Interim Analyses and in Section 8.8 Multiplicity.

Protocol/Amendment No.: 394-06

Table 12 Analysis Strategy for Key Efficacy Hypotheses

Endpoint/Variable (Description, Time Point)	Statistical Method [†]	Analysis Population	Missing Data Approach
Primary Hypothesis			
OS	Test: Stratified Log- rank test Estimation: Stratified Cox model with Efron's tie handling method.	ITT	Censored at the last date the subject was known to be alive
Secondary Endpoints	l		

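### The TTP censoring table applies the new-therapy cut only to subjects who neither progress nor die, so whether time after a switch counts depends on the later outcome

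*Protocol*

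**What the plan says.** Protocol section 8.6.1.5, Table 10, has five rows. Four matter here:

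- **Event row.** "PD documented after ≤ 1 missed disease assessment" is an event at the PD date. New therapy is not mentioned.
- **Missed-assessment row.** "PD documented after ≥ 2 missed disease assessments" is censored because of the missed scans. New therapy is not mentioned.
- **Switch without PD or death.** "No PD and no death; new anticancer treatment is initiated" leads to "Censored at last non-PD disease assessment before new anticancer treatment".
- **Death without PD.** "Censored at date of randomization or date of last non-PD disease assessment, whichever is later". New therapy is not mentioned.

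The text above the table uses the PD date "regardless of discontinuation of study drug. Unlike in PFS analysis, death is not considered as an event". That deals with stopping study drug, not with starting another treatment.

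The neighbouring endpoints are handled differently. In the primary PFS analysis (Protocol Table 9), PD counts only if it precedes new therapy, and the censoring row covers "PD or death documented after ≥2 consecutive missed disease assessments or after new anticancer therapy, if any". DOR (Protocol Table 11) does the same: "Death or progression after ≥2 consecutive missed adequate disease assessments or after new anti-cancer therapy" is censored.

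SAP section 3.5.1.5, Table 2, rewords two TTP rows slightly but adds no new-therapy condition to the PD or death rows. SAP Tables 1 and 3 keep that condition for PFS and DOR.

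**The concern.** Take two subjects who start the same new therapy on the same day without PD. One has PD on a later scan with at most one missed assessment. That subject stays at risk through the new therapy and is an event. The other neither progresses nor dies, and is removed at the last scan before the switch. At the time of the switch nobody can say which rule applies, because the choice depends on the future.

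This keeps the post-switch events and discards much of the event-free time that belongs with them, so the estimated TTP hazard rises. It rises more in the arm with more pre-progression switching, which can move the HR either way. A single scan can also be a TTP event and a censoring in primary PFS. TTP has one analysis column and no sensitivity analysis that would reveal the problem.

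**Working it through.** **1. The tables side by side** (subjects who start new therapy before PD)

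| Analysis | PD seen after new therapy | No PD, no death | Consistent? |
|---|---|---|---|
| PFS primary (Table 9) | censored before new therapy | censored before new therapy | yes |
| PFS sensitivity 1 (Table 9) | event | censored at last assessment, new therapy ignored | yes |
| DOR (Table 11) | censored before new therapy | censored before new therapy | yes |
| TTP (Table 10; SAP Table 2) | event | censored before new therapy | **no** |

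The TTP death row has the same gap. A switcher who is scanned and then dies without PD keeps time up to the last scan. One who survives does not.

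**2. Can PD be documented after a switch?** Scheduled imaging stops at new therapy (Protocol 2.1, 7.1.4.3, 7.1.4.4). Three routes remain:
- Switching before central verification of PD is discouraged, not barred (2.1).
- Off-schedule images that capture progression go to the central vendor (7.1.4.1).
- The discontinuation scan has a ±4-week window (7.1.4.4), and new therapy can start within 30 days of the last dose (7.1.1.6).

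**3. Anchors.** The documents give no planning figure for TTP. The nearest is PFS (Protocol 8.9): control median 1.5 months, HR 0.65, 395 events, one-sided α 0.2%. Check: √(395 × 2/3 × 1/3) × |ln 0.65| − 2.878 = 9.369 × 0.431 − 2.878 = 1.16, so power is 0.877 against the stated 88%. These values serve as a proxy for TTP.

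**4. Simulation.** Exponential times, 2:1 allocation, Cox HR, 200,000 to 300,000 subjects per scenario, follow-up of 3 to 31 months, switching independent of PD risk. *Written* is Table 10 as it stands. *Consistent* censors every switcher at new therapy. Ignoring new therapy for everyone gave the same answer as *consistent* in the 3%, 5% and 10% scenarios, within simulation error.

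| Control median (months) | True HR | Switching per month, pembrolizumab / placebo | Switchers still scanned | Written | Consistent | Shift |
|---|---|---|---|---|---|---|
| any | any | any | none | – | – | 0 |
| 1.5 | 0.65 | 3% / 10% | all | 0.641 | 0.644 | −0.003 |
| 1.5 | 0.65 | 10% / 3% | all | 0.661 | 0.652 | +0.009 |
| 1.5 | 0.65 | 5% / 20% | all | 0.643 | 0.649 | −0.006 |
| 1.5 | 0.65 | 20% / 5% | all | 0.668 | 0.652 | +0.016 |
| 6 | 0.65 | 5% / 5% | all | 0.676 | 0.652 | +0.024 |
| 6 | 0.65 | 3% / 10% | all | 0.596 | 0.647 | −0.051 |
| 6 | 0.65 | 10% / 3% | half | 0.744 | 0.654 | +0.090 |
| 6 | 0.65 | 10% / 3% | all | 0.783 | 0.652 | +0.131 |
| 6 | 1.00 | 5% / 5% | all | 0.999 | 0.998 | +0.001 |
| 6 | 1.00 | 3% / 10% | all | 0.902 | 0.999 | −0.097 |
| 6 | 1.00 | 10% / 3% | all | 1.104 | 0.995 | +0.109 |

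What matters is the amount of switching before PD. Equal monthly rates still give a shift at HR 0.65 (the 5% / 5% row), because the arm that progresses later has longer in which to switch.

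**5. Why the follow-up assumption matters.** With progression hazard λ, switching rate ν, and every switcher scanned for w months, the written rule multiplies events per person-time by

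[λ + ν(1 − q)] / [λ + ν(1 − q − qλw)], with q = exp(−λw).

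This factor is 1 at w = 0 (no scans) and tends to 1 as w grows (every switcher's PD is eventually seen). The distortion lies between. For w = 12 weeks = 2.76 months, 1.5-month median, switching 20% / 5%:

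- Pembrolizumab: λ = 0.300, q = 0.436, qλw = 0.362. Factor = (0.300 + 0.2 × 0.564) / (0.300 + 0.2 × 0.202) = 0.413 / 0.341 = 1.21.
- Placebo: λ = 0.462, q = 0.279, qλw = 0.356. Factor = (0.462 + 0.05 × 0.721) / (0.462 + 0.05 × 0.365) = 0.498 / 0.480 = 1.04.
- HR ≈ 0.65 × 1.21 / 1.04 = 0.76.

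Simulating the 12-week case gave 0.75, against 0.67 with 3 to 31 months of follow-up.

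**The case against.** The strongest reply is that the protocol largely prevents the data that would cause harm. A subject who starts new therapy moves to survival follow-up (7.1.1.6), which is telephone contact about every 12 weeks (7.1.6.3.3). Switching before centrally verified PD is discouraged, so most switches should come after a TTP event. With no post-switch scans the written rule and the PFS/DOR rule give identical results. At the 1.5-month median with only 10% of switchers still scanned, the shift was about 0.01 or less in every scenario tried, including the 12-week one. All of this stands, and it makes the bias conditional.

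It is also fair that Table 10 counts post-switch PD by omission. A reader might infer a deliberate choice to follow subjects through new therapy. The documents do not support that: such a rule would not censor non-progressors at the switch, and PFS sensitivity analysis 1 shows how the sponsor writes it when it is intended.

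A reader might also infer that TTP and PFS cannot be compared because of this gap. They already differ by design, since death is not a TTP event, and the contrast drawn here is only with the primary PFS analysis.

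None of this closes the gap in the text. No TTP wording in either document limits the event row to PD before new therapy.

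**Conclusion.** The TTP rule is internally inconsistent as written, in both documents. That conclusion rests on the table rows alone.

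The size of the effect is not settled by the documents. It is zero if no scan after new therapy reaches central review. If scans continue, the simulated HR shift is at most about 0.01 to 0.02 at a 1.5-month control median with 3 to 31 months of follow-up. It reaches about 0.13 under an assumed 6-month median with unequal switching. A short window for seeing post-switch PD can also enlarge it. Switching rates, scanning rates and follow-up are assumptions, and the 1.5-month median is a PFS figure used as a proxy.

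A reader might go further and infer that the reported TTP HR will be biased, or biased towards pembrolizumab. The documents support neither: the shift can be nil, and its sign depends on which arm switches more. TTP is a secondary endpoint with no hypothesis in Protocol section 3.2, and section 8.8 controls alpha only for OS, PFS and ORR. No trial decision turns on it, so this is a minor correction.

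**What to change.** In Protocol Table 10 and SAP Table 2, change three rows:

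1. **Event row:** after "PD documented after ≤ 1 missed disease assessment", add *and before new anticancer therapy, if any*.
2. **Missed-assessment row:** extend it to *PD after two or more consecutive missed assessments, or after new anticancer therapy*, censored at the last non-PD assessment before the earlier of the two.
3. **Death row:** censor at the later of randomization and the last non-PD assessment *before new anticancer therapy, if any*.

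The third edit is needed because the first two alone would leave outcome-dependent censoring among switchers who die without PD. Together the edits bring TTP into line with primary PFS and DOR.

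Ignoring new therapy in every row, as PFS sensitivity analysis 1 does, would be equally consistent. The sponsor should choose one rule and state it.

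The cost is three table rows in each document and the matching programming. No new data are needed, and if PD after a switch proves rare the results will hardly change.
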